14	CONFLICT OF INTEREST POLICY	15
15	REFERENCES	17
16	ATTACHMENTS	17

CONFIDENTIAL

This material is the property of the NYU School of Medicine and Langone Medical Center. Do not disclose or use except as authorized in writing by the study sponsor

List of Abbreviations

AE	Adverse Event/Adverse Experience
CFR	Code of Federal Regulations
CRF	Case Report Form
CSOC	Clinical Study Oversight Committee
DCC	Data Coordinating Center
DHHS	Department of Health and Human Services
DSMB	Data and Safety Monitoring Board
FFR	Federal Financial Report
FWA	Federalwide Assurance
GCP	Good Clinical Practice
HIPAA	Health Insurance Portability and Accountability Act
ICF	Informed Consent Form
IRB	Institutional Review Board
ISM	Independent Safety Monitor
MOP	Manual of Procedures
N	Number (typically refers to participants)
NIH	National Institutes of Health
OHRP	Office for Human Research Protections
OHSR	Office of Human Subjects Research
PI	Principal Investigator
QA	Quality Assurance
QC	Quality Control
SAE	Serious Adverse Event/Serious Adverse Experience
SOP	Standard Operating Procedure
US	United States

CONFIDENTIAL

This material is the property of the NYU School of Medicine and Langone Medical Center. Do not disclose or use except as authorized in writing by the study sponsor

Protocol Summary

[figure not shown]
Title	Calcific Tendonitis Treatment-Barbotage vs. Barbotage with Cortisone Injection: A Randomized Controlled Double-Blind Study
Short Title	Calcific Tendonitis Treatment-Barbotage vs. Barbotage with Cortisone Injection
Protocol Number	S19-01299
Population	A sample size of 140 patients belonging to NYU Langone Health with calcific tendonitis will be enrolled including both genders, ages 18-90.
Objectives	The purpose of this study is to determine the efficacy of barbotage therapy by comparing the clinical and sonographic changes in patients that solely receive barbotage to patients receiving the standard of care, barbotage with cortisone injection.
Study Center(s)	Single-center, prospective study
Number of Subjects	We will aim to enroll a total of 140 subjects.
Study Duration	The estimated duration of the study is 24 months.
Subject Participation Duration	Each patient will be present for the day of treatment and follow-up at: 6 weeks, 3 months, and 6 months. Patients will be in the study for 6 months.
Estimated Time to Complete Enrollment	The estimated time to completion of enrollment is 24 months.

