5.1 Study Procedures/Evaluations

Once the study team member arrives to the physician office, they will provide the potential patient subjects with information on the study and ask the patient for their consent to be in the study. The patient will be given shoulder-related questionnaires (ASES and QuickDASH), asked to complete a VAS survey and will receive a shoulder radiograph prior to treatment and at 6 months post-treatment, to evaluate the state of the condition.

Patients in this study will receive the assigned form of treatment and have assigned follow-up appointments at 6 weeks, 3 months and 6 months post-treatment. The alternative treatment (barbotage with saline injection) will be administered in the same fashion as the control (barbotage with cortisone injection). If the patient desired to solely have the standard therapy, they will be ineligible for the study.

Patients will be randomized to one of two cohorts: receiving barbotage with saline injection or receiving barbotage with cortisone injection. Both groups will follow the same protocol for standard of care: 4 mg of dexamethasone (if receiving cortisone) and barbotage. Cortisone dosing is consistent with FDA-approved guidelines. The saline used for the barbotage and sham injection are the same, and readily available in the procedure room. The saline is manufactured by B. Braun Medical, available in the procedural room, and will be equivalent in volume to that of the cortisone injection, determined by the performing physician. [name] will be performing the procedure. At each follow-up appointment, the patients will complete the questionnaires and VAS scores. Patients and physicians will be blinded to the cohort; patients will be randomly chosen by the research study members excluding the primary investigator (PI). The barbotage

CONFIDENTIAL

This material is the property of the NYU School of Medicine and Langone Medical Center. Do not disclose or use except as authorized in writing by the study sponsor

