and cortisone/saline (sham) injection will occur concurrently by a different physician from the PI, blinding the PI and patients. The study team members responsible for randomization will converse with the [name], who will be in charge of performing the barbotage and cortisone/saline (sham) procedure. The associated research members and the physician performing the barbotage excluding the PI and patients are the only individuals who will be aware of the blind. Blinding will be maintained until a patient experiences adverse effects, in which case the researchers will inform the primary physician.

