8.2 Measures to Minimize Bias

8.2.1 Enrollment/Randomization/Masking Procedures

Patients will be randomized (1:1) using REDCap. The physicians and patients will be blinded to their assigned treatment group.

As each patient receives the barbotage, the patient nor the PI will not know if they are receiving the cortisone in addition to the barbotage. Study team members and [name] will not be blinded and in position to randomize the patients. [name] will not be blinded to the study as she is performing the procedures. [name], the PI, and his patients will be blinded from which combination of the two they receive (barbotage and cortisone or saline/sham).

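### The unblinded operator performs the lavage that both arms share, and nothing withholds the allocation from her until that lavage is finished

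*Combined protocol and SAP*

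**What the plan says.** The title describes "A Randomized Controlled Double-Blind Study". The details on blinding are in sections 5.1 and 8.2.1.

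- **Who delivers treatment.** In 5.1 the barbotage and the cortisone or saline "injection will occur concurrently by a different physician from the PI, blinding the PI and patients". The same physician does both steps.
- **Who tells her.** Also in 5.1: "The study team members responsible for randomization will converse with the" physician in charge of the procedure.
- **Who knows the arm.** Besides the research members, "the physician performing the barbotage excluding the PI and patients are the only individuals who will be aware of the blind" (5.1). Section 8.2.1 agrees that the operator "will not be blinded to the study as she is performing the procedures".
- **Who does not know.** In 8.2.1, "the patient nor the PI will not know if they are receiving the cortisone in addition to the barbotage".
- **What should keep the arms alike.** "The alternative treatment (barbotage with saline injection) will be administered in the same fashion as the control" (5.1). Section 5.1 adds that both groups follow one standard-of-care protocol, and that the saline "will be equivalent in volume to that of the cortisone injection, determined by the performing physician".

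Sections 5.1 and 8.2.1 each also state, without exception, that physicians are blinded. That does not fit the unblinded operator described in the same two sections.

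**The concern.** The lavage is an active treatment given to everyone, and it depends on the operator's judgement: how much to wash, how many passes to make, when to stop. The trial can isolate the steroid only if the lavage is delivered alike in both arms. An operator who knows that no steroid will be given may wash more to compensate, or less, without intending to.

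If so, the between-arm difference in pain and deposit size is a steroid effect plus a lavage effect. Blinding the patient and the PI does not prevent this, because the difference arises in delivery and not in reporting. With no record of the lavage planned, no later analysis could detect it or adjust for it.

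**Working it through.** **1. Does the operator know the arm?** Yes. Sections 5.1 and 8.2.1 both say so, and neither lists her among those kept blind during the barbotage.

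**2. When does she learn it?** Not stated. Section 5.1 gives no time for the conversation with the randomising staff. Section 5.2.2 lists randomisation among the Visit 1 items without stating an order and without mentioning the intervention. Attachment A ticks randomisation and intervention in the same visit column. The wording in 8.2.1 can be read as giving the time of her unblinding or the reason for it. What can be established is narrower: no sentence keeps the arm from her until the lavage ends, and 5.1 describes lavage and injection as concurrent.

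**3. Is the lavage fixed by the protocol?** No. Sections 5.1, 5.1.1 and 5.1.2 name the procedure but give no lavage volume, number of passes, aspiration end point or record of what was done.

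**4. Does the lavage reach the endpoints?** Yes, on the protocol's own account. Section 1.2 attributes symptom relief to irrigating and aspirating the deposit. Section 3.2.1 expects the deposit to shrink by at least 10% after aspiration and lavage. Pain on VAS and deposit size both appear under the primary endpoints in 3.2.1.

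**5. What could a shift do? (illustration only)** The documents give no figure for such a bias, so the shift δ is an assumption.

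- Inputs: 140 enrolled (8.1) at 1:1 (8.2.1) gives 140/2 = 70 per arm. Losing the 10 per group allowed in 8.1 leaves 70 − 10 = 60.
- Plan's own figure: 8.1 states more than 128 patients for d = 0.6, power 0.80, alpha 0.05. The normal formula 2(1.96 + 0.842)²/d² gives 44 per arm at d = 0.6 (45 with the t distribution), so 88 to 90 in total. The stated 128 matches d = 0.5 (64 per arm with the t distribution). That mismatch is a separate matter; the rejection rates below use only the numbers per arm.
- Formula: a two-sample t test, two-sided 5%, with no true steroid effect and noncentrality δ√(n/2). For δ = 0.2 this is 0.2 × √30 = 1.10 at n = 60 and 0.2 × √35 = 1.18 at n = 70.

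| Assumed shift δ | Rejection rate, 60 per arm | Rejection rate, 70 per arm |
|---|---|---|
| 0 | 5% | 5% |
| 0.1 SD | 8.4% | 9.0% |
| 0.2 SD | 19.2% | 21.7% |

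If the shift instead opposed a true d of 0.6, the observable effect would be 0.6 − 0.1 = 0.5 or 0.6 − 0.2 = 0.4. At 64 per arm, power would fall from 92% to 80% or 61%.

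**The case against.** The best defence is that 5.1 commits to treating both groups under one protocol and in the same manner, that a single named physician does the procedures, and that the documents openly say who is unblinded. Operators often cannot be masked. Patients, who report the VAS, are blinded, and so is the PI. No difference in lavage has been shown.

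Much of this stands. A single operator removes between-operator variation, and the harm is a risk, not a finding. But the commitment to equal treatment states an intention that no procedure enforces, and the person relied on to carry it out knows the arm. Nor is this a case where masking is impossible: she needs the allocation, at most, at the injection step.

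Three stronger readings are tempting but not supported:

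- *She is told before the lavage begins.* This is a likely inference, but no passage fixes the time.
- *The patient's blind is compromised by talking with an unblinded operator.* No passage describes such talk. The only conversation described is between the randomising staff and the operator.
- *Her choice of injection volume lets the barbotage differ by arm.* That discretion concerns the injection, not the lavage, and 5.1 already requires equivalent volumes. The sentence naturally means the volume a cortisone injection would have had. All that remains is that the text does not say how equivalence is ensured.

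**Conclusion.** The concern holds as a preventable risk of performance bias. An unblinded operator delivers an unspecified treatment common to both arms, one that acts on symptoms and on the radiographic endpoint, and nothing delays her knowledge of the arm until that treatment is complete. The conclusion rests on the text of 5.1 and 8.2.1 and does not require her to have been told at any particular moment.

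The size and direction of any bias are unknown. The rise from 5% to about 19% to 22% depends wholly on an assumed 0.2 SD shift; it is generic arithmetic, not an estimate for this trial. A reader should not infer that the arms will be treated differently, or that patient-reported pain is collected unblinded. Separately, the statements that physicians are blinded contradict the description of the operator and must be reconciled.

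**What to change.** In 5.1 and 8.2.1:

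1. Run the REDCap allocation, or disclose it to the operator, only after she has declared the lavage complete. Section 5.1 already places the baseline scores and X-ray before treatment, so they are unaffected.
2. Where feasible, have an already unblinded team member who is permitted to do so hand over the assigned injection in a covered, identically labelled syringe. If the two preparations look alike, the operator may then stay masked throughout.
3. Reconcile the statements that physicians are blinded with the unblinded operator, naming by role who is and is not blind. Clarify how equivalent injection volume between arms is ensured; no particular volume is proposed here.

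The cost is protocol wording and a small change in workflow. An unblinded team member must be at hand during the procedure, with a short pause before the injection. Unblinded staff already exist, but the documents do not say whether they may prepare or handle injections, so item 2 needs local confirmation. Item 1 does not depend on it. The change is needed before enrolment, because unequal lavage cannot be corrected afterwards.

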5.1.1 Standard of Care Procedures

- Medical history (Past medical/surgical history, previous imaging)
- Medication history (e.g., previous medications)
- Follow-up at 6 weeks, 3 months and 6 months
- U/S guided barbotage
- Pre and post visual analog scale scores
- Pre and post ASES Shoulder Index
- Pre and post QuickDASH
- Baseline Shoulder X-Ray

5.1.2 Standard of Care Study Procedures

Patients with calcific tendonitis are prescribed a variety of treatment options including medicinal, procedural and operative. Barbotage with cortisone injection therapy is a standard of care treatment for patients with calcific tendonitis who fail primary, minimally invasive therapy. Both the control and experimental cohort will follow-up with their physician at the assigned times. Shoulder X-Rays are part of the standard of care.

5.2 Study Schedule

5.2.1 Screening

Screening (Day -7 to -1)

- Review medical history to determine eligibility based on inclusion/exclusion criteria.
- Review medications history to determine eligibility based on inclusion/exclusion criteria.

5.2.2 Enrollment/Baseline

Enrollment/Baseline Visit (Visit 1, Day 0)

- Obtain informed consent of potential participant verified by signature on study informed consent form.
- Physical exam
- Randomize into treatment cohort or control cohort
- Schedule follow-up visits
- Record VAS, ASES Shoulder and QuickDASH scores.
- Perform Shoulder Series X-Ray

5.2.3 Intermediate Visits

Intermediate Visits (Week 6, Month 3)

- Follow-up visits
- Record VAS

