Statistical Methodology	Statistical analysis will be performed using ANOVA or t tests. Pearson's correlation will be used to determine relationship between outcomes scores.

CONFIDENTIAL

This material is the property of the NYU School of Medicine and Langone Medical Center. Do not disclose or use except as authorized in writing by the study sponsor

Drug/Device Template Version: 13 JUN 2016

Schematic of Study Design

CONFIDENTIAL

This material is the property of the NYU School of Medicine and Langone Medical Center. Do not disclose or use except as authorized in writing by the study sponsor

1 Introduction, Background Information and Scientific Rationale

1.1 ***Background Information and Relevant Literature***

Calcific tendonitis is a disorder characterized by pain and development of calcium deposits on one or more rotator cuff tendons and affecting normal sleeping habits and routine daily activities. Inflammation associated with the calcium deposit is theorized to contribute to the pain [1]. A few studies state the prevalence of the condition has been reported to be 3 to 10% in the general population [2, 3]. Several treatment modalities exist including anti-inflammatory and analgesic, extra-corporeal shockwave therapy (ESWT), ultrasound-guided needling and lavage (barbotage), and surgical treatment are in use. However, a consensus to which treatment is superior nor most effective does not exist.

1.2 ***Rationale***

Ultrasound-guided barbotage is a safe and efficient form of therapy for calcific tendonitis, with slightly more than half of the patients experiencing pain relief [4]. The procedure involves percutaneous insertion of a needle with saline, washing and aspirating the fluid content of the joint. By irrigating and aspirating the calcium deposit, symptomatic relief is achieved and signs of pathological resolution is seen on sonogram. All of this is achieved while preserving the native tendon, potentially avoiding surgery. Barbotage with cortisone injection continues to be the standard of care for calcific tendonitis resistant to physical therapy and cortisone injection, but it is not known if barbotage alone can provide the same amount of clinical and symptomatic resolution. We would like to evaluate and witness any significant difference from the standard treatment of care.

1.3 ***Potential Risks & Benefits***

1.3.1 ***Known Potential Risks***

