3.2 Study Endpoints

3.2.1 Primary Study Endpoints

The primary study endpoint will focus on the decrease in pain of the affected shoulder measured by VAS scores. Based on their responses and their scores at the time prior to and after their barbotage therapy begins, we can determine a primary endpoint with a 10% change between baseline and their final visit. We would also like to observe the affected rotator cuff tendon and measure the efficacy of barbotage therapy via shoulder radiograph. Shoulder X-Ray is considered standard of care and we expect a resolution in size of the calcified deposit by at least 10% after aspiration and lavage.

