5.2.4 Final Study Visit

Final Study Visit (End of Month 6)

- Record VAS, ASES Shoulder, and QuickDASH scores.
- Perform Shoulder Series X-Ray for Research Purposes

CONFIDENTIAL

This material is the property of the NYU School of Medicine and Langone Medical Center. Do not disclose or use except as authorized in writing by the study sponsor

6 Assessment of Safety

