8.1 Sample Size

We will aim to enroll a total of 140 subjects. According to a post hoc power analysis calculating the effect size using our preliminary data, >128 patients are required with $d=0.6$ to obtain a power of 0.80 and an alpha value of 0.05. Therefore we are including an additional 10 patients per group to account for patients that may be lost to follow up. Statistical analysis will be performed using chi-squared and/or fisher's exact testing depending on size for binary variables. Continuous variables will be compared with paired t-tests if the data is approximately normally distributed. If the data is not normally distributed, Mann-Whitney tests will be used. All protected health information will be removed prior to statistical analysis.

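### A normality check decides whether the primary VAS test is within patients or between the randomised arms, and no planned analysis adjusts for baseline VAS

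*Combined protocol and SAP*

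**What the plan says.** Section 3.2.1 makes pain the primary outcome: "The primary study endpoint will focus on the decrease in pain of the affected shoulder measured by VAS scores". It ties the endpoint to two time points, "with a 10% change between baseline and their final visit".

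VAS is collected four times. Section 5.2.2 (baseline) has "Record VAS, ASES Shoulder and QuickDASH scores", section 5.2.4 (month 6) has "Record VAS, ASES Shoulder, and QuickDASH scores", and section 5.2.3, under "Intermediate Visits (Week 6, Month 3", adds VAS at the two interim visits. The Schedule of Events agrees.

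The analysis is described in two places:

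- Section 8.1: "Continuous variables will be compared with paired t-tests if the data is approximately normally distributed". Then: "If the data is not normally distributed, Mann-Whitney tests will be used".
- Protocol Summary, Statistical Methodology: "Statistical analysis will be performed using ANOVA or t tests".

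Neither place says whether the test is applied to scores or to changes, at which visit, or with which factors or covariates. No section gives the week-6 and month-3 VAS a stated analytic role. The only rule that bears on missing data is in section 4.7.2: a withdrawn patient's information is removed from the database and another patient is enrolled.

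**The concern.** The two branches in section 8.1 are not two ways of testing one hypothesis. A paired t-test works on differences within a patient, here most naturally month 6 minus baseline. It does not compare two independent randomised groups. A Mann-Whitney test does. The normality check on the trial data therefore selects the question as well as the statistic. It also moves the target from a mean change to an ordering of ranks.

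This matters because the Protocol Summary sets out to compare barbotage alone with barbotage plus cortisone. Patients in both arms could improve from the shared procedure or with time alone. A significant paired test would then say nothing about what the cortisone adds, yet section 2.1, which speaks of the efficacy of barbotage without cortisone, could be read as satisfied by it.

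A second, smaller issue is efficiency. Baseline VAS is collected on every patient, and adjusting for it makes the arm comparison more precise, but no section does so.

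**Working it through.** **Which question each named test answers**

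| Source | Test | Compares |
|---|---|---|
| 8.1, data look normal | paired t-test | two measurements in the same patients |
| 8.1, otherwise | Mann-Whitney | two independent groups |
| Protocol Summary | ANOVA or t tests | not stated |

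Only the second row is clearly a between-arm test. This part needs no numerical assumption.

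**The plan's own sample-size figure.** Section 8.1 gives d = 0.6, power 0.80, alpha 0.05 and more than 128 patients. Sidedness is not stated; I assume two-sided. The two-sample normal formula is n per arm = 2(1.96 + 0.84)²/d².

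- d = 0.6: 43.6, so 44 per arm; the t calculation gives 45 per arm, 90 in total.
- d = 0.5: 62.7, so 63 per arm; the t calculation gives 64 per arm, 128 in total.

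The stated 128 matches d = 0.5, not d = 0.6, so I show both.

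**Patients at month 6.** 140/2 = 70 per arm, less the plan's allowance of 10 per group, leaves 60.

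**Assumptions.** d is in units of the SD of a single VAS score. The correlation r is the same between any two visits. The documents do not give r, so I use 0.3, 0.5 and 0.7.

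**Baseline adjustment at month 6.** Relative to an unadjusted month-6 comparison (factor 1), the variance factor is 1 − r² for ANCOVA and 2(1 − r) for a change score. The effective n per arm is 60 divided by the factor. Power is from the noncentral t distribution with noncentrality d√(effective n/2), using 118 degrees of freedom for the unadjusted and change-score tests and 117 for ANCOVA.

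| | r = 0.3 | r = 0.5 | r = 0.7 |
|---|---|---|---|
| ANCOVA variance factor | 0.91 | 0.75 | 0.51 |
| Variance cut | 9% | 25% | 49% |
| ANCOVA effective n per arm | 65.9 | 80.0 | 117.6 |
| Power, d = 0.5: unadjusted | 77.5% | 77.5% | 77.5% |
| Power, d = 0.5: change score | 63% | 77.5% | 94% |
| Power, d = 0.5: ANCOVA | 81% | 88% | 97% |
| Power, d = 0.6: unadjusted | 90% | 90% | 90% |
| Power, d = 0.6: ANCOVA | 93% | 96% | 99.5% |

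**What the interim visits add.** Suppose 10 per arm miss month 6 but have week-6 and month-3 VAS. Given baseline, the correlation between two follow-up visits is ρ = r/(1 + r) = 0.231, 0.333, 0.412. The share of month-6 variance explained by the two interim visits is R² = 2ρ²/(1 + ρ) = 0.087, 0.167, 0.240. A repeated-measures model with a month-6 contrast cuts the variance, relative to ANCOVA on the 60 completers, by R²(1 − 60/70) = R²/7 = 1.2%, 2.4%, 3.4%. In power this is less than one percentage point at either d.

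**The case against.** The best defence is that the plan is loosely worded rather than wrong. The summary names ANOVA, the Mann-Whitney branch is a between-group test, and the word paired may be a slip for a two-sample t-test. At the stated d = 0.6, an unadjusted comparison of 60 per arm already has 90% power, above the 80% target. Section 3.2.1 uses change from baseline, so baseline is not ignored. Its 10% figure can also be read as a responder threshold, in which case the chi-squared or Fisher test in section 8.1 would apply.

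Much of this stands, and it limits the point:

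- A reader might infer that the trial will never compare its arms. The documents do not support that: the stated purpose is a comparison and one branch makes it. What is missing is a single fixed test that does so.
- A reader might infer that the plan throws baseline away. It does not; a change score or a paired test uses it. Only covariate adjustment is absent.
- A reader might infer that leaving out the week-6 and month-3 scores costs substantial power. For a month-6 comparison it does not; nearly all the gain comes from baseline. Nor do the documents exclude a role for those visits; they state none.
- A reader might infer that a repeated-measures model would rescue all missing data. It cannot use records that section 4.7.2 removes, so it helps only for patients who miss month 6 without withdrawing.

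The defence does not remove the main fault. The summary's ANOVA has no stated factors and adds a further candidate test. The responder reading adds another. If paired is a slip, it still has to be corrected, and the data-driven switch would remain.

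**Conclusion.** The concern holds in this form: the primary VAS test is not fixed in advance, one of the two branches in section 8.1 does not compare the randomised arms, and collected baseline VAS is not used as a covariate. The first two parts rest on the text alone.

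The size of the third depends on a correlation that the documents do not give, on equal correlation between visits, on 60 per arm at month 6, and on d being scaled to a single VAS score. Within r = 0.3 to 0.7, the gain in power over an unadjusted month-6 test runs from about 4 to 19 percentage points at d = 0.5, and from about 2 to 9 at d = 0.6. These figures do not show that the trial is underpowered at its stated effect size. The change is worth making mainly because it fixes the question before the data are seen; the added precision is a further benefit.

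**What to change.** Align the Protocol Summary (Statistical Methodology), section 3.2.1 and section 8.1 on one primary analysis: the between-arm difference in VAS at month 6, adjusted for baseline VAS, with a 95% CI, reported whatever a normality check shows. Say in 3.2.1 what role, if any, the 10% change plays, so that it does not compete as a second primary analysis.

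Either of two models will do, but name one:

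- ANCOVA of month-6 VAS on arm and baseline VAS; or
- a repeated-measures model of VAS at week 6, month 3 and month 6 with arm, visit, arm-by-visit and baseline VAS, taking the month-6 contrast as primary. This also keeps patients who miss month 6 without withdrawing. Cross-refer to section 4.7.2, because removed records cannot enter the model.

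Remove the paired t-test as the arm comparison, and keep a two-sample rank test only as a sensitivity analysis. The cost is wording in three places and slightly more analysis work. No new data, visits or patients are needed.
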